6.1 Sample Size Estimation

6.1.1 Randomized Trial

The sample size for the randomized trial has been estimated to be 50 patients per treatment group in order to have 90% power to detect at least a 0.60 D difference in myopia progression between treatment groups allowing for 10% loss to follow up. An adjustment for treatment group crossover was not made as this was very infrequent in COMET (2 out of 469 children) and is expected to be similarly infrequent in COMET2.

6.1.2 MEM and Nott Accommodation Ancillary Study

The sample size for the ancillary study has been estimated to be 300 patients. This sample size is based on the number of patients needed to have 0.05 half-widths for 95% confidence intervals for point estimates of sensitivities and specificities of 90%.

6.2 Statistical Analysis

6.2.1 Randomized Trial

6.2.1.1 Primary Analysis

The primary analysis will be a comparison of the average change from baseline to 3 years in amount of myopia between children in the single-vision lens group and the children in the progressive-addition lens group.

The primary outcome is change from baseline to 3 years in spherical equivalent refractive error (SER) in diopters (D) as measured by cycloplegic autorefraction. For each eye, the Grand Seiko autorefractor will yield 5 readings consisting of sphere, cylinder, and axis. Each reading will be converted to a spherical equivalent refractive error (SER) and the median of the 5 SER values will be used for analysis.

The primary analysis will be a treatment group comparison of mean 3-year change in amount of myopia using the t-test. For each time point, the spherical equivalent refractive error (SER) values for a given child will be calculated using the average of the spherical equivalent refractive errors from each eye. Change in amount of myopia will be calculated as the difference of the child's SER at 3 years minus the child's SER at baseline.

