135 the study on the basis of their having certain characteristics including high accommodative lag, it
136 is felt that some form of disclosure is warranted. At the patient's next study visit, the
137 investigator will inform the patient and parent that the patient may not have as much difficulty
138 focusing (accommodating) as was previously thought. In addition to verbally conveying this
139 information, parents will be given a written IRB-approved disclosure statement. Parents and
140 patients will be encouraged to have the patient stay in the study but will have the option to
141 withdraw. Masking of treatment group will be maintained regardless of whether the patient
142 continues in the study or opts to withdraw.

143

144 Primary Analysis

145 The primary analysis will include data from all randomized patients, regardless of whether the
146 patient meets the revised accommodative response criterion.

147

148
149
150
151
152
153
154
155
156
157
158
159
160
161
162
163
164
165
166
167
168
169
170

CONTACT INFORMATION

COORDINATING CENTER

[name]., Ph.D. (Director)
Jaeb Center for Health Research
[name]
[name]
[contact]PEDIG or [contact]
[contact]PEDIG or [contact]

PROTOCOL CHAIR

[name].
The New England College of Optometry
[name]
[contact]

| | | |
|-----|----------------------------------------------------------------------|-----|
| 171 | CHAPTER 1: BACKGROUND AND SUMMARY | 1-1 |
| 172 | 1.1 Objective | 1-1 |
| 173 | 1.2 Rationale | 1-1 |
| 174 | 1.3 Synopsis of Study | 1-1 |
| 175 | 1.4 Study Screening/Enrollment Summary Flowchart | 1-3 |
| 176 | 1.5 Randomized Trial Summary Flowchart..... | 1-4 |
| 177 | CHAPTER 2: SCREENING/ENROLLMENT..... | 2-1 |
| 178 | 2.1 Eligibility Assessment and Informed Consent..... | 2-1 |
| 179 | 2.2 Screening..... | 2-1 |
| 180 | 2.2.1 Non-cycloplegic Procedures | 2-1 |
| 181 | 2.2.2 Eligibility for Screening with Cycloplegic Autorefraction..... | 2-2 |
| 182 | 2.2.3 Cycloplegic Autorefraction..... | 2-3 |
| 183 | 2.3 Randomization | 2-3 |
| 184 | 2.4 Prescribing Spectacles | 2-4 |
| 185 | 2.5 Obtaining Spectacles..... | 2-4 |
| 186 | CHAPTER 3: FOLLOW-UP | 3-1 |
| 187 | 3.1 Visit Schedule | 3-1 |
| 188 | 3.2 Protocol Visits..... | 3-1 |
| 189 | 3.2.1 Examination Procedures | 3-1 |
| 190 | 3.2.2 Masking of Treatment Group..... | 3-2 |
| 191 | 3.3 Additional Visits | 3-2 |
| 192 | 3.4 Treatment During Follow Up..... | 3-2 |
| 193 | 3.4.1 Prescription Changes | 3-2 |

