273 whether refractive error in each eye is within the eligibility range of -0.75 to -2.50 D spherical
274 equivalent.

275
276 Once the patient's eligibility has been verified by cycloplegic autorefraction, the trial will be
277 further discussed with the patient's parent or guardian and written informed consent for the
278 randomized trial will be obtained.

279
280 A summary of the screening/enrollment process is shown in the flowchart in section 1.4.

281 Randomization

282
283 Each patient entering the randomized trial will be randomly assigned to one of two treatment
284 groups: Progressive addition lenses (PALs) with a +2.00 D addition, or single vision lenses
285 (SVLs). Spectacles will be prescribed and paid for by the study.

286
287 The sample size for the primary analysis for the trial is estimated to be 100 children, with
288 approximately half of the children randomized to PALs and the other half randomized to SVLs.

289 Follow-up

290
291 Children will have three years of follow up, with visits every 6 months. At each visit a
292 subjective refraction will be performed to assess whether a prescription change is needed,
293 accommodative response will be measured using an open field autorefractor, and oculomotor
294 alignment will be assessed. At the one-, two-, and three-year visits, the primary outcome
295 measurements of cycloplegic autorefraction will be taken.

[figure not shown]
296
297 A summary of the randomized trial is shown in the flowchart in section 1.5.

298 **1.4 Study Screening/Enrollment Summary Flowchart**

SCREENING CRITERIA

[figure not shown]
- Age 8 to <12 years
- Refractive error determined by subjective refraction without cycloplegia meeting all of the following:
 - Amount of myopia: -0.50 to -3.00 D in each eye
 - Astigmatism ≤ 1.5 D in each eye
 - Anisometropia ≤ 1.00 D difference between eyes in sph. eq.
- No strabismus by cover/uncover test at far, near, and/or near with +2.00D over best subjective refraction
- Visual acuity of at least 20/20 with best subjective refraction in both eyes
- No current or prior use of PALs, bifocals, or contact lenses in either eye (prior or current use of SVLs is allowed)
- No history of any of the following:
 - Strabismus, amblyopia, or nystagmus
 - Any ocular or systemic medications known to affect accommodation
 - Any ocular surgery which might influence refractive development
 - Any ocular, systemic, or neuro-developmental condition that might influence refractive development

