3.2.1.1 Additional Procedure at Annual Visits

At annual visits, cycloplegic autorefraction of both eyes will be performed using the Grand Seiko autorefractor after administration of 1% tropicamide.

503 Cycloplegic autorefraction should be performed after all other examination procedures have been
504 completed.

505

506 **3.2.2 Masking of Treatment Group**

507 At all visits, the investigator will be masked to the patient's treatment group. Patients will remove
508 their spectacles prior to the exam and will not wear the spectacles for any exam procedures.

509

510 **3.3 Additional Visits**

511 In order to maintain masking of the study investigator, any time the patient reports any type of
512 problem (e.g. blurry vision, headaches, etc.), a visit should be scheduled for an examination by
513 an unmasked consulting clinician.

514

515 The procedures and assessments to be completed for this examination are at the discretion of the
516 consulting clinician. A subjective refraction can be performed if the consulting clinician
517 suspects that the refractive error may not be optimally corrected. Other clinical procedures as
518 outlined in the protocol can be used to assess the nature of the problem and to arrive at a viable
519 treatment.

520

521 The patient's spectacle prescription may be changed if indicated (see section 3.4.1). On rare
522 occasions in which the patient's problem is not resolved by a change in spectacle prescription,
523 and the consulting clinician feels that a change in lens type (i.e. treatment crossover) may be
524 warranted, the consulting clinician should contact the protocol chair to discuss the case.
525 Prescribing a change in lens type will be permitted only with prior approval of the protocol chair.

526

527 **3.4 Treatment During Follow Up**

528 The patient should wear the random-assigned spectacles during all waking hours. Contact lenses
529 should not be worn.

530

531 Vision therapy may not be prescribed.

532

533 **3.4.1 Prescription Changes**

534 A prescription change must be made if the subjective refraction finding differs from the
535 current prescription by at least 0.50 D in spherical equivalent. Prescription changes can
536 be made for smaller differences at investigator discretion if the new prescription
537 improves the patient's visual acuity by at least one line over that in their current spectacle
538 correction. Whenever a spectacle change is made, spectacles will be prescribed according

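### The primary t-test on 3-year change leaves the year-1 and year-2 cycloplegic readings and the baseline and randomisation factors unused; a longitudinal model would be a cheap, modest improvement

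*Protocol*

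**What the plan says.** Section 6.2.1.1 fixes the comparison, the method and the outcome:

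- Comparison: "The primary analysis will be a comparison of the average change from baseline to 3 years in amount of myopia".
- Method: "The primary analysis will be a treatment group comparison of mean 3-year change in amount of myopia using the t-test".
- Outcome: "Change in amount of myopia will be calculated as the difference of the child's SER at 3 years minus the child's SER at baseline".

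The test has no covariates, although section 2.3 stratifies randomisation by site and by previous spectacle wear.

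The same measurement is taken every year. Section 3.2.1.1 says: "At annual visits, cycloplegic autorefraction of both eyes will be performed using the Grand Seiko". The synopsis (section 1.3) counts all three annual readings as primary outcome measurements: "At the one-, two-, and three-year visits, the primary outcome". Section 6.2.1.2 uses the year-1 and year-2 values for secondary estimates of change with 95% confidence intervals.

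On loss, the sample size in section 6.1.1 is set to detect 0.60 D "between treatment groups allowing for 10% loss to follow up". Section 4.1 cites 98.5% retention at 3 years in the earlier COMET trial and expects withdrawal to be very infrequent. Section 4.2 allows a child to be discontinued for ineligibility or substantial protocol deviations.

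On the analysis population, Amendment #2 says: "The primary analysis will include data from all randomized patients". That sentence goes on to say that inclusion does not depend on whether the "patient meets the revised accommodative response criterion".

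Chapter 6 refers further statistical detail to separate documents, which are not at hand.

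**The concern.** A difference between two time points needs both values. If a child misses the 3-year visit and nothing is imputed, that child has no outcome and leaves the primary comparison, even with cycloplegic readings at years 1 and 2. Those readings should predict the missing value well, because they are the same measurement on the same child.

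Two things are at stake.

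- **Precision.** Information already collected is not used in the primary test.
- **Bias.** If loss is related to progression, and differently so in the two arms, the mean difference among children seen at 3 years is shifted. A model that uses the earlier readings removes the part of that shift which they explain.

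The protocol leaves some routes to loss open: ordinary withdrawal, discontinuation under section 4.2, and the disclosure with an option to withdraw that Amendment #2 offers to children above the revised accommodative response limit.

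**Working it through.** **Inputs from the protocol.** 50 children per arm, 90% power, difference 0.60 D, 10% loss allowance (6.1.1); 98.5% retention in the earlier trial, so 1.5% loss (4.1).

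**Assumed, because the protocol does not give them.** Two-sided alpha 0.05; the SD, back-solved below; the correlation r between 3-year change and earlier change, 0.7 to 0.9; how lost children differ from those retained.

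**Step 1: the plan's own figure.** Evaluable children per arm = 50 × (1 − 0.10) = 45. Solving for the SD that gives 90% power at 0.60 D with 45 per arm yields 0.878 D (normal approximation) or 0.868 D (t distribution). Going the other way, an SD of 0.87 D needs 45 per arm, and 45 / 0.90 = 50. So 50 per arm is attainable, but it cannot be confirmed without the SD and alpha. It fits a test on observed 3-year values with the loss already budgeted.

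**Step 2: power of the t-test on observed values (SD 0.868 D).**

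| Loss | n per arm | Power |
|---|---|---|
| 0% | 50 | 92.8% |
| 1.5% | 49.25 | 92.4% |
| 10% | 45 | 90.0% |

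**Step 3: power if earlier readings are used.** For a fraction f missing at year 3 completely at random, in children who have earlier readings, effective n = 50 / [1 + (f / (1 − f)) × (1 − r²)]. For f = 0.10 and r = 0.8 this is 50 / [1 + 0.111 × 0.36] = 50 / 1.04 = 48.1.

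| Loss | r | Effective n | Power | Gain over t-test (points) |
|---|---|---|---|---|
| 10% | 0.7 | 47.3 | 91.4% | 1.4 |
| 10% | 0.8 | 48.1 | 91.8% | 1.8 |
| 10% | 0.9 | 49.0 | 92.3% | 2.3 |
| 1.5% | 0.7 | 49.6 | 92.6% | 0.2 |
| 1.5% | 0.9 | 49.9 | 92.7% | 0.3 |

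This counts only the recovery of missing 3-year values. Any gain from adjusting for baseline SER and the randomisation factors is not included, because the protocol gives no correlation for it.

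**Step 4: bias from selective loss.** In one arm, the bias of the observed mean = fraction lost × (mean of lost − mean of retained). Suppose only one arm loses selectively and its lost children progress 0.5 to 1 SD more, that is 0.43 to 0.87 D.

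- 10% loss: 0.10 × 0.43 = 0.04 D to 0.10 × 0.87 = 0.09 D, or 7% to 15% of 0.60 D.
- 1.5% loss: 0.015 × 0.43 = 0.006 D to 0.015 × 0.87 = 0.013 D, or 1% to 2% of 0.60 D.

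If both arms lose the same fraction with the same excess progression, the two shifts cancel. With unequal loss of 15% and 5% and an excess of 0.5 to 1.0 D in both arms, the net bias is (0.15 − 0.05) × 0.5 = 0.05 D to (0.15 − 0.05) × 1.0 = 0.10 D.

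**The case against.** The strongest case against is that a t-test on a prespecified single-time-point change is a valid primary analysis in a randomised trial that expects very little loss. The 10% in section 6.1.1 is a planning margin, not a forecast; section 4.1 gives the forecast. Near 1.5% loss the gain is trivial, and even at 10% the sample size already pays for the lost children. The one-arm selective loss in Step 4 has no support in the protocol. A mixed model also adds no post-baseline information on a child lost before year 1. All of this stands, and it limits the point to an improvement.

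The detailed plan might also impute missing 3-year values, since a t-test can be run on imputed data. That is possible, and the lack of a missing-data rule in the protocol is not raised here. What remains is that the protocol has chosen a two-time-point, unadjusted method when a better one uses data already scheduled.

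Three stronger readings are tempting, and the protocol does not support them.

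- *The t-test contradicts the all-randomised rule in Amendment #2.* It does not. That sentence settles whether children enrolled under the old accommodative response limit stay in the analysis; it does not address missed visits.
- *The year-1 and year-2 data are discarded.* They are left out of the primary test only; section 6.2.1.2 reports them.
- *A quarter of the trial is being invited to leave.* The roughly 25% refers to those randomised by the date of the amendment. Families are encouraged to stay, and masking is kept. The disclosure follows a baseline measurement and applies in both arms, so it gives no evident reason for loss to differ by lens type.

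**Conclusion.** The point holds as a cheap improvement; section 6.2.1.1 is not in error. As written, and without imputation, the primary test omits children who lack a 3-year reading and makes no use of their annual readings. It also leaves out baseline SER and the factors on which randomisation was stratified.

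The effect is negligible if retention matches the earlier trial and modest if the 10% allowance is used up. The bias figures rest on assumed selective loss in one arm. A likelihood-based model would remove only the part explained by observed SER, so they are upper limits on what the change could correct in those scenarios. The power figures rest on the assumed alpha, the back-solved SD and the assumed correlations. The reason to act is protection against selective loss at almost no cost; the power gain alone would hardly justify it.

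**What to change.** In section 6.2.1.1 and the detailed analysis plan, make the primary test the 3-year treatment contrast from a longitudinal model of SER at years 1, 2 and 3. Include treatment-by-visit terms, and adjust for baseline SER and the randomisation factors: previous spectacle wear, and site, with small sites pooled or site fitted as a random effect. The target stays the same, namely the difference between arms in mean change at 3 years. Keep the t-test on observed 3-year change as a sensitivity analysis.

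State the missing-at-random assumption that the model makes. It would also help to say that the all-randomised sentence in Amendment #2 refers to the accommodative response criterion, and that 3-year readings are still sought from children discontinued under section 4.2.

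The cost is a change of wording, slightly more analysis work and one assumption to defend. The model itself needs no extra visits or measurements.

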239 The overall 3-year difference in progression between children wearing PALs vs SVLs in the
240 Correction of Myopia Evaluation Trial (COMET) was 0.20D, statistically significant but not
241 clinically meaningful.¹
242

243 Reduced accommodative responses in association with near work has been shown in previous
244 research to be a factor in the development and progression of myopia.²⁻⁴ The COMET study
245 found in a secondary analysis that children with larger accommodative lags (> 0.43D for a 33
246 cm target, based on a median split) wearing single vision lenses (SVLs) had the most
247 progression at 3 years, and that progressive addition lenses (PALs) were effective in slowing
248 progression in these children, with statistically significant adjusted 3-year treatment effects
249 for those with larger lags in combination with near esophoria (0.64D), or lower baseline
250 myopia (0.48D).⁵ The treatment effects also were observed in these groups at 1 year and
251 became larger from 1-3 years. These results suggest that PALs are a clinically-viable
252 spectacle treatment for slowing progression in myopic children with large accommodative
253 lags in conjunction with near esophoria and lower amounts of myopia.
254

255 **1.3 Synopsis of Study**

256 Screening / Eligibility

257 Patients aged 8 to <12 years old who are suspected of having myopia in the range of -0.50D to
258 - 3.00D will be invited to be screened for the randomized trial.
259

260 The screening procedures will be explained and the parent or guardian of each patient will give
261 written informed consent for screening before any screening-specific procedures are performed.
262 Approximately 700 children are expected to be screened.

263
264 Screening consists of non-cycloplegic procedures of subjective refraction, testing of oculomotor
265 alignment, and testing of accommodative response. Measurement of accommodative response
266 using the Grand Seiko autorefractor is part of the screening for the randomized trial. Patients at
267 participating sites also will be asked to complete two additional tests of accommodation by
268 MEM and Nott retinoscopy as part of an ancillary study.

269
270 Once the above non-cycloplegic screening procedures are completed, patients who are ineligible
271 for the randomized trial will terminate participation in the study. Patients who *appear to be*
272 *eligible* for the randomized trial then will undergo cycloplegic autorefraction to determine

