397 3. Accommodative response at near (33 cm) is less than 2.00D by non-cycloplegic autorefraction

- 398 4. No strabismus present by cover-uncover test at far, near, and/or near with +2.00D over best
399 subjective refraction
- 400 5. Near esophoria (≥ 2.0 PD) present by alternate prism and cover test (APCT) at near using
401 best refractive correction determined from non-cycloplegic subjective refraction
- 402 6. No current or prior use of PALs, bifocals, or contact lenses in either eye (prior or current use
403 of SVLs is allowed)
- 404 7. No history of any of the following:
- 405 • Strabismus
 - 406 • Amblyopia
 - 407 • Nystagmus
 - 408 • Ocular, systemic, or neuro-developmental condition that might influence refractive
409 development
 - 410 • Ocular surgery which might influence refractive development
 - 411 • Ocular or systemic medications known to affect accommodative response, such as
412 atropine, pirenzepine, and anti-epileptic medications
 - 413 • Diabetes or seizures
- 414 8. Birth weight at least 4.5lbs
- 415

416 **2.2.3 Cycloplegic Autorefraction**

417 If the patient is eligible for screening with cycloplegic autorefraction, this procedure will be
418 performed on both eyes using the Grand Seiko autorefractor after cycloplegia with 2 drops of 1%
419 tropicamide.

- 420 • The protocol for this procedure is described in the Testing Procedures Manual.
- 421

422 Patients are considered eligible for the randomized trial if the refractive error obtained by
423 cycloplegic autorefraction meets all of the following:

- 424 • Spherical equivalent: -0.75 to -2.50 D in each eye
 - 425 • Astigmatism ≤ 1.5 D in each eye
 - 426 • Anisometropia ≤ 1.00 D difference between eyes in spherical equivalent
- 427

428 **2.3 Randomization**

429 Each patient enrolling in the randomized trial will be randomly assigned to one of two treatment
430 groups:

- 431 • Progressive addition lenses (PAL) with a +2.00D addition
 - 432 • Single vision lenses (SVL)
- 433

434 The JAEB Center will construct a master randomization list using a permuted block design
435 stratified by site and by whether the patient has previously worn spectacles, which will specify
436 the order of treatment group assignments.

437

438 The patient's treatment group assignment can be obtained either by completing randomization on
439 the PEDIG website or by contacting the Jaeb Center if internet access is down.

440

441 **2.4 Prescribing Spectacles**

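### The primary t-test leaves out the two randomisation strata and uses baseline refraction only by subtraction; a pre-specified ANCOVA is a cheap gain in precision, not a repair of validity

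*Protocol*

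**What the plan says.** - **Primary test (Protocol 6.2.1.1).** "The primary analysis will be a treatment group comparison of mean 3-year change in amount of myopia using the t-test". No stratum and no covariate is named.
- **Outcome (6.2.1.1).** "Change in amount of myopia will be calculated as the difference of the child's SER at 3 years minus the child's SER at baseline". Baseline is therefore subtracted, but it is not a term in a model.
- **Randomisation (2.3).** The coordinating center will "construct a master randomization list using a permuted block design", "stratified by site and by whether the patient has previously worn spectacles".
- **Sample size (6.1.1).** "The sample size for the randomized trial has been estimated to be 50 patients per treatment group", for "90% power to detect at least a 0.60 D difference in myopia progression between treatment groups", "allowing for 10% loss to follow up". Neither the SD nor alpha is given.
- **Secondary analyses (6.2.1.2).** Prior spectacle wear and baseline refractive error appear again only as subgroup factors.

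The opening of Chapter 6 refers to separate documents for detail. The choice of an unadjusted t-test is nevertheless made in the protocol itself, so it is a stated choice and not a gap left to the SAP.

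**The concern.** Stratified blocking makes the arms alike in site mix and prior spectacle wear. If those factors are related to progression, the difference between arm means varies less from one randomisation to the next than it would under simple randomisation. A pooled two-sample t-test does not know this. It still counts the variation between strata as random error, so its standard error overstates the true one. Type I error then falls below nominal and the confidence interval is wider than it need be.

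Baseline SER is a related but separate matter. Subtracting it removes its one-for-one contribution to the 3-year value. Any remaining dependence of change on starting refraction stays in the error term, although baseline SER is measured in every randomised child.

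What is at stake is precision in a trial planned at 50 children per arm.

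**Working it through.** **1. The plan's own figure.** Of 50 per arm, 10% loss leaves 50 × 0.9 = 45 evaluable. The SD and alpha are not stated, so I assume two-sided 0.05 and solve for the SD that gives 90% power at 0.60 D:

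SD = 0.60 × √(45/2) / (1.960 + 1.282) = 0.60 × 4.743 / 3.242 = 0.878 D (normal approximation); the noncentral t gives 0.868 D.

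Forward, an SD of 0.87 D needs 45 per arm, and 45/0.9 = 50. The stated size is thus coherent with an unadjusted comparison at an SD of about 0.87 D. It cannot be confirmed independently.

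**2. Simple formula for adjustment.** If the covariates explain a share R² of the variance, the residual SD is 0.878 × √(1 − R²). Power at 0.60 D with 45 per arm:

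| Assumed R² | Residual SD (D) | Power |
|---|---|---|
| 0 | 0.878 | 90.0% |
| 5% | 0.856 | 91.4% |
| 10% | 0.833 | 92.7% |
| 20% | 0.785 | 95.2% |

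Reading the gain off against 90% overstates it where the variance lies in the strata, because stratified blocking also makes the unadjusted estimate less variable. With 10% from strata and perfect balance:

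- unadjusted power = Φ((3.24 − 1.96)/√0.9) ≈ 91%
- adjusted power = Φ(3.24/√0.9 − 1.96) ≈ 92.7%
- type I error of the t-test = 2 × (1 − Φ(1.96/√0.9)) = 3.9%

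The gain is then about 1.5 points, not 2.7. The 3.9% is a limiting case, since incomplete blocks in small strata weaken the balance.

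**3. Simulation of both analyses.** Permuted blocks of 4 within site × prior wear, 90 evaluable children, SD 0.878 D, 4000 runs per setting. The 8 sites, the block size and the R² values are assumptions. The ANCOVA uses prior wear, baseline and fixed site effects.

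| R² strata | R² baseline | Mean t-test SE (true SE) | Type I error, t-test | Power, t-test | Power, ANCOVA | Gain (points) |
|---|---|---|---|---|---|---|
| 0 | 0 | 0.185 (0.185) | 5.4% | 89.9% | 88.7% | −1.2 |
| 5% | 0 | 0.185 (0.180) | 4.6% | 89.2% | 89.5% | +0.3 |
| 10% | 5% | 0.184 (0.181) | 4.7% | 89.7% | 92.5% | +2.8 |
| 20% | 5% | 0.184 (0.172) | 3.8% | 91.9% | 95.5% | +3.6 |
| 30% | 10% | 0.183 (0.164) | 2.9% | 92.7% | 98.1% | +5.4 |

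True SE and type I error are from the runs without a treatment effect. Monte Carlo error is about 0.3 to 0.5 points. The 30% plus 10% row shows the direction; nothing in the protocol supports so strong a relation.

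**4. How the site term matters.** The number of sites is not stated. With 100 children, 10% loss, strata explaining 10% and fixed site effects, power for t-test against adjusted analysis was:

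- 8 sites: 90.5% against 91.9%
- 15 sites: 91.0% against 91.2%
- 25 sites: 90.5% against 86.8%

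With no prognostic value, fixed effects for 25 sites cost about 5 to 6 points. Adjusting only for prior wear and baseline SER cost under 1 point in that situation.

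**The case against.** The strongest reply is that nothing is broken. A t-test on a change score is valid under this randomisation, any error is on the conservative side, and the sample size agrees with an unadjusted analysis. Amendment 2 lets enrolment reach 150, all to be analysed, which may add power. Eligibility is narrow (cycloplegic SER of -0.75 to -2.50 D), which limits what baseline SER can explain. Careless adjustment can also hurt, as the 25-site result shows. All of this stands. It sets the size of the point but does not remove it.

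Four stronger readings are tempting, and the protocol does not support them:

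- **Baseline refraction is ignored.** It is subtracted in the change score; only its use as a covariate is missing. A chance baseline imbalance matters only so far as change depends on baseline.
- **Power is certainly given away.** The protocol gives no R². If the factors explain nothing, the t-test standard error is right and adjustment costs about a point.
- **The trial is underpowered or its type I error is inflated.** Neither follows. Power agrees with the plan under the assumptions above, and type I error can only fall.
- **Resting on COMET's adjusted effects while estimating an unadjusted one is a flaw.** The rationale (1.2) does cite effects "with statistically significant adjusted 3-year treatment effects" of 0.64 D and 0.48 D. For a difference in means in a randomised trial, adjusted and unadjusted analyses target the same quantity, so the contrast is not a defect.

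The unseen SAP may contain an adjusted sensitivity analysis. That would not change which analysis the protocol names as primary.

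**Conclusion.** The point holds as a conditional loss of efficiency. The protocol stratifies on two factors and then fixes a primary test that uses neither, with baseline SER as a subtraction only. If the factors are prognostic, the standard error is somewhat too large, the test is conservative and precision is lost.

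At 0.60 D the gain from adjustment is roughly 2 to 4 power points if the factors explain 15 to 25% of the variance, negligible at about 5%, and about 1 point is lost at zero. These figures rest on 45 evaluable per arm, two-sided alpha 0.05 (assumed), an SD of about 0.87 D (back-solved), and assumed R² values, site count and block size. This is a free or cheap improvement, not an error of validity and not a shortfall against the planned power.

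**What to change.** In 6.2.1.1, and correspondingly in the SAP, pre-specify the primary analysis as an ANCOVA of 3-year SER change on treatment, baseline SER, prior spectacle wear and site. Enter site as a random effect or with small sites pooled by a rule fixed in advance, not as fixed effects for many small sites. Report the adjusted treatment difference with its 95% CI, and keep the t-test as a supportive analysis.

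The change needs a sentence or two, made before any treatment comparison of 3-year data, and no new data: all the covariates are already collected at screening or used at randomisation. The downside is a small loss of degrees of freedom, worth about 1 power point if the covariates turn out to be uninformative.
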